***Correcting Residual Errors With Spectral, Ultrasound, Traditional Speech Therapy
(C-RESULTS-RCT)***

Protocol NCT03737318

Updated 12/8/2025

MASTER PROTOCOL FOR C-RESULTS RCT

Goal of study: Compare response to two types of visual biofeedback (ultrasound and visual-acoustic) versus traditional motor-based treatment for residual speech errors.

Primary outcome measure: Acoustically measured accuracy of within-session trials from Phase I (Acquisition).

Secondary outcome measure: Perceptually rated accuracy after Phase II (Generalization).

Functional outcome measure: Socioemotional questionnaire before vs after treatment.

Hypothesis: Mixed-effects models investigating the primary outcome measure will show a significant advantage for biofeedback over traditional motor-based treatment as early as the first day of Phase 1, and no later than the final day.

Enrollment: Target 55 kids in each of 2 sites (MSU, Syracuse), total n = 110

0. Pre-screening

- Phone screening to ask about all major exclusionary categories
 - Use Phone Screening Script
 - Additionally, review Parent Questionnaire for any responses that do not meet exclusionary criteria specified in Phone Screening Script.

1. Evaluation Session 1:

- Goal: Determine eligibility for inclusion in study; collect baseline measures for use in predicting response to treatment.
- See "Checklist for C-RESULTS Evaluation - Day 1"
 - Consent and assent; parent history form, demographic and socio-emotional questionnaires
 - Must be between 9;0 and 15;11 at time of enrollment.
 - Must have been exposed to English no later than age 3.
 - English must have equal or dominant status. Balanced bilinguals are okay.
 - Must speak a rhotic dialect of English; presence of one or more non-rhotic speakers in the home is exclusionary.
 - ADHD is admissible; other neurobehavioral disorders (ASD, OCD, Tourette's) are exclusionary.
 - History of CAS / learning disability / dyslexia is admissible if participant meets cutoff scores on eval day 1. Other developmental disorders are exclusionary.
 - History of permanent hearing loss is exclusionary. Temporary hearing loss due to otitis media, including recurrent OM/tubes, is admissible.
 - Hearing screening in soundbooth at 20 dB HL (500 Hz, 1000 Hz, 2000 Hz, and 4000 Hz)—must identify 2/3 tones at 20 dB at each frequency for inclusion.

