- Goal: Evaluate change in time since treatment; administer perturbation tasks (NYU/MSU only) and accompanying perception tasks (all sites).
- See 1-Checklist for CRESULTS_Evaluation_PostTx2_RCT_ALLTasks (NYU/MSU) or 1-Checklist for CRESULTS_Evaluation_PostTx2_RCT_NoPerturbation (Syracuse) in CRESULTS Planning Folder/4c - Evaluation_COVID_CRESULTS/Post-Tx Evaluation 2 - RCT
- Probes for /r/ (if a child is being evaluated more than 6 weeks post treatment, don't administer probes; use 1-Checklist for CRESULTS_Evaluation_PostTx2_RCT_NoProbes)
- Head-had identification task
- Head-had discrimination task
- Reflexive perturbation task (NYU/MSU only)
- Adaptive perturbation task (NYU/MSU only)

12. Analysis Plan

- All analyses will be conducted following the intent-to-treat principle. For participants who drop out, missing data will be multiply imputed based on information collected about them prior to their loss to follow-up.
- For our primary outcome (Acquisition), we will fit a multilevel model with measures nested within study participants and words. The dependent variable will be F3-F2 distance in /r/ targets produced in each day of Phase 1 treatment. The primary independent variable of interest is group (traditional motor-based treatment versus biofeedback, with visual-acoustic and ultrasound biofeedback types pooled for this analysis). The model will also adjust for site, performance response category based on Dynamic Assessment (high responder versus low responder), acquisition day (1, 2, or 3, treated as categorical), and pre-treatment accuracy (mean F3-F2 distance across /r/ sounds in the word probe elicited in the first pre-treatment evaluation). If a within-session time trend is supported by the data, we will extend the model to account for time trends across trials within each day of treatment. Random intercepts will be included to reflect the fact

MASTER PROTOCOL FOR C-RESULTS RCT

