To assess impact on our primary outcome, the acoustic accuracy measure of F3-F2 distance, we will fit a multilevel model using Phase 1 (Acquisition) data. The primary effect of interest is a comparison between MBT and biofeedback treatments, with visual-acoustic and ultrasound biofeedback types pooled for this analysis. This initial model will also adjust for site, performance response category (high responder versus low responder based on a Dynamic Assessment), Acquisition day (1, 2, or 3), and pre-treatment accuracy (mean F3-F2 distance across /i/ sounds in the word probe elicited in the first pre-treatment evaluation). If a within-session time trend is supported by the data, we will extend the model to account for time trends across trials within each day of treatment. Random intercepts will be included to reflect the fact that observations are nested within speakers and words, and random slopes that improve overall model fit (for speaker, acquisition day; for word, performance response category and pre-treatment accuracy) will be retained following model comparison using likelihood ratio tests.

Likelihood ratio tests will also be used to test the hypothesis of an advantage for biofeedback over MBT. Tests will be performed in two different model specifications. In one, the overall effect across days will be tested by focusing on the coefficient on the treatment variable. The other specification will interact the treatment variable with time in order to test whether the effect varies across days, since the hypothesized advantage for biofeedback over MBT could emerge as early as the first day or as late as the third day of Phase 1 (Acquisition). Although a positive effect of biofeedback is hypothesized, two-sided hypothesis tests will be used to be conservative.

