Our second analysis will fit a linear mixed-effects model using word probe data collected in one immediate pre-treatment and one immediate post-treatment session. The outcome variable will reflect the proportion of naïve listeners who rated the /i/ sound in a given production as correct. The model will include an indicator for time point (pre- versus post-treatment) and for treatment group (biofeedback versus MBT), as well as the interaction between them. As was the case for our primary measure, the model will adjust for site, performance response category based on Dynamic Assessment, and pre-treatment accuracy. Random intercepts for speaker, item (the 50 target words making up the probe measure), and listener will be included. Random slopes of response category and pre-treatment accuracy on word will be examined and included only as warranted by model comparison. As above, likelihood ratio tests will be used to assess the significance of the overall treatment effect. Again, while a positive effect of biofeedback is hypothesized, we will use a two-sided hypothesis test to be conservative.

For this second model, we will additionally test for the presence of a significant time-by-condition interaction in which the magnitude of improvement associated with biofeedback significantly is allowed to vary with time. If we observe a difference in our primary measure (Acquisition) but not our secondary measure (Generalization), this will be interpreted as evidence that biofeedback is more efficient, but not more effective, than MBT.

The final analysis will evaluate changes in impact scores from the 11-item survey assessing the social, emotional, and academic consequences of RSE from pre- to post-treatment time points. A mixed model similar to that used in the previous analyses will be fit including time (pre- versus post-treatment), treatment group (biofeedback versus MBT), and the time-treatment interaction as the primary predictors. The model will also adjust for site, performance response category based on Dynamic Assessment, and pre-treatment accuracy. We will again estimate the interaction between time and treatment group to evaluate whether the functional impact of treatment differs across biofeedback versus MBT conditions.

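### The plan's reading of a difference in Acquisition but not in Generalization compares two different instruments, so the discordance may reflect the change of measure

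*Combined protocol and SAP*

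**What the plan says.** Acquisition is judged acoustically. Section 12 (Analysis Plan) says: "The dependent variable will be F3-F2 distance in /r/ targets produced in each day of Phase 1 treatment". The Data analysis plan at the end of the document agrees: "To assess impact on our primary outcome, the acoustic accuracy measure of F3-F2 distance, we will fit a multilevel model using Phase 1 (Acquisition) data".

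Generalization is judged perceptually, from "word probe data collected in one immediate pre-treatment and one immediate post-treatment session". In the Data analysis plan's second analysis, "The outcome variable will reflect the proportion of naïve listeners who rated the" target sound in a production as correct.

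The second analysis then sets a rule that links the phases: "If we observe a difference in our primary measure (Acquisition) but not our secondary measure (Generalization), this will be interpreted as evidence" that biofeedback is the more efficient method without being the more effective one. I call this the efficiency-only reading. The rule appears in the Data analysis plan but not in Section 12. It carries no caveat about the change of measure.

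The plan does apply the acoustic measure to the word probe once, as a baseline covariate: "mean F3-F2 distance across /r/ sounds in the word probe elicited in the first pre-treatment evaluation". Section 9 also flags the 9th trial of each Generalization block for acoustic measurement. Neither is used in a planned comparison of groups at or after Generalization.

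**The concern.** The efficiency-only reading is a statement about time: an early advantage for biofeedback that is no longer there at the end. Supporting it requires one measure that shows the advantage early and fails to show it late. Here the phase and the measure change together. Three situations give the same pattern of test results:

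- the advantage was present early and has gone;
- the advantage is still present acoustically, but the listener measure misses it;
- the gain was acoustic throughout, and listeners would not have heard it even in Acquisition.

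The rule reports the first in every case. The trial could therefore state that biofeedback speeds learning with no better end result while the acoustic difference at the end is as large as it was at the start.

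**Working it through.** The documents give no effect size, SD, significance level, power or margin, so there is no stated figure to reproduce. The check asks how often the triggering pattern would arise if the true effect were the same in both phases.

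**Inputs from the documents.** The target is 110 children (55 at each of two sites), allocated 3:3:4. With the two biofeedback arms pooled this gives 0.6 × 110 = 66 against 0.4 × 110 = 44. Tests are two-sided.

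**Assumptions.** Significance level 5%; true effect 0.6 SD in both phases; correlation ρ between the two test statistics from 0 to 0.6; child-level comparison of two means instead of the planned mixed models. If an instrument has relative sensitivity q (in variance terms), its effect is 0.6 × √q.

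**Formulae.** SE = √(1/66 + 1/44) = 0.1946. At full sensitivity the expected z is 0.6 / 0.1946 = 3.083, and power is 0.869. The pattern is P(Z₁ > 1.96 and |Z₂| ≤ 1.96), with Z₁ the acoustic and Z₂ the listener statistic, from a bivariate normal with correlation ρ.

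**Hand check at ρ = 0.** With equal sensitivity: 0.869 × (1 − 0.869) = 0.114. With the listener measure at q = 0.4, its effect is 0.6 × √0.4 = 0.379 SD and its power 0.496, so 0.869 × (1 − 0.496) = 0.438.

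**Results.** In each range the first figure is for ρ = 0 and the second for ρ = 0.6.

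| q of the weaker instrument | Its effect (SD) | Its power | Pattern if the listener measure is weaker | Pattern if the acoustic measure is weaker |
|---|---|---|---|---|
| 1.0 (equal) | 0.600 | 0.869 | 11.4% to 7.5% | 11.4% to 7.5% |
| 0.8 | 0.537 | 0.787 | 18.5% to 13.7% | 10.3% to 5.5% |
| 0.6 | 0.465 | 0.666 | 29.1% to 23.7% | 8.7% to 3.4% |
| 0.4 | 0.379 | 0.496 | 43.8% to 38.9% | 6.5% to 1.6% |

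The equal-sensitivity row is ordinary sampling error and would occur with a single instrument. Only the departure from that row belongs to the change of measure. With the listener measure weaker, the excess is about 6 to 7 percentage points at q = 0.8 (13.7 − 7.5; 18.5 − 11.4), 16 to 18 at 0.6 and 31 to 32 at 0.4. With the acoustic measure weaker, the departure is negative.

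**The case against.** **The direction is not known.** A reader might infer that the listener measure is the blunter one, because it is bounded and entry requires no more than 30% on the word probe. The documents do not support that. The 30% limit is a clinician-rated entry criterion, whereas the group contrast depends on naive-listener scores after 3 Acquisition and 16 Generalization sessions. Nor is the acoustic measure obviously richer: one flagged trial in 10, at the targeted 150 to 200 trials, gives 15 to 20 tokens a session, or 45 to 60 over three sessions, against 50 words each scored by several listeners. This objection stands, and is why both directions are shown.

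**Listeners are the endpoint that matters.** The protocol chose perceptual accuracy for Generalization. If a difference at the end cannot be heard, calling biofeedback no more effective is defensible. This stands as a reason to keep the listener outcome. It does not support the rule's implied account of an early advantage that went away.

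**An acoustic analysis of the word probe would not equalise the phases.** A reader might infer that it would separate instrument from phase completely. It would not. Acquisition uses within-session trials on five practised syllables and tests a group effect across days; the probe has 50 words and tests a time-by-group interaction. Material, setting and estimand would still differ. The flagged Generalization trials are closer in setting, but their difficulty adapts to the child's performance, so they are a weaker basis for comparing groups.

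**The rule is one interpretive sentence.** True: no primary estimate or test depends on it. It is nevertheless a pre-set conclusion, and followed as written it can be unsupported.

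**Conclusion.** The concern holds in a limited form. The two phases are analysed on different instruments, no planned analysis bridges them, and the plan still draws a conclusion across them. A discordant result can therefore reflect the change of measure, and the planned analyses could not show whether it did.

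The size and direction are unknown. Under the stated assumptions the pattern occurs in about 8% to 11% of trials from sampling error alone, in 14% to 44% if the listener measure has 80% to 40% of the acoustic measure's sensitivity, and in 2% to 10% if the acoustic measure is the weaker. The equal effect of 0.6 SD after 3 sessions and after 19 is itself an assumption.

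Two stronger readings should be resisted. The 44% is not an error rate for this trial: it is one end of an assumed range, and part of it is sampling error. Nor do the documents show that post-treatment recordings are never measured acoustically, only that no such analysis is planned. The primary test is unaffected.

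**What to change.** - Keep listener-rated accuracy as the Generalization outcome.
- Compute F3-F2 distance on the same immediate pre- and post-treatment word-probe recordings. Fit the second-analysis model to it as a supportive analysis, without the listener random intercept, which has no acoustic counterpart.
- Reword the rule so that the efficiency-only conclusion is not drawn when the post-treatment word probe shows a group difference in F3-F2. State in advance what counts as a difference, for example the time-by-group term at the primary test's two-sided level, which the plan should also state. In that case, report that the acoustic advantage persisted but was not detected by listeners.
- If neither measure shows a group difference, report both estimates with confidence intervals. Note that material and setting also differ between the phases, and that non-significance alone does not show equal effectiveness.

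The cost is SAP wording plus acoustic processing and alignment checks on existing recordings: at most 50 × 110 = 5,500 productions per session. If the immediate pre-treatment session is the first evaluation, that set is already due to be measured for the covariate. No new visit or rater is needed. The other cost is a more cautious conclusion.

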 - Probes for /r/: Sentence, Word, Stimulability
 - Rake-wake discrimination task
 - Bite block task
 - Category goodness task
 - Phonetic awareness task

4. Treatment targets

- Target variants:
 - syllabic /ɛ/, vocalic front vowel context, vocalic back vowel context, consonantal front vowel context, consonantal back vowel context.
- All participants will practice all variants in all phases of treatment.

5. Phase 0: Dynamic assessment

- Dynamic Assessment will consist of a single 90-minute session of traditional motor-based (non-biofeedback) instruction. The goal is to evaluate participants’ stimulability in detail and classify them into stimulability categories for randomization.

MASTER PROTOCOL FOR C-RESULTS RCT

- Same protocol as Phase I: Acquisition (see below), including both pre-practice and structured practice, but with no biofeedback.
 - Instruction (~25 min): Discuss tongue shapes for /r/. Use “Script_Introducing tongue shapes for r_Dynamic_Assessment_CRESULTS,” plus Tiede et al poster, followed by 2-minute break.
 - Pre-practice (until performance criterion met or session-level timer reaches 44 minutes): Relatively unstructured practice guided by the Prepractice Tally Sheet, with model and KP on every trial, followed by a 2-minute break.
 - Structured syllable practice (44 min).
- Based on the treating clinicians’ perceptual ratings of participants’ performance in Phase 0, participants will be categorized as high responders (>5% accuracy during Dynamic Assessment) or low responders (0-5% accuracy).

6. Randomization

- Overview:
 - Randomization will be supervised by the study statistician at the central site (NYU).
 - Randomization will be stratified by site and severity.
 - Randomization will be proportioned in a 3:3:4 ratio (ultrasound biofeedback : visual-acoustic biofeedback : traditional motor-based treatment) at each site.
- Approach:
 - The study statistician will generate confidential participant treatment assignments in batches of 10, where each batch of 10 corresponds to a combination of site (Montclair State University versus Syracuse University) and response category (high versus low).
 - Random assignments will be generated to ensure the following distribution per batch: 3 individuals assigned to receive visual-acoustic biofeedback, 3 to receive ultrasound biofeedback, and 4 to receive MBT.

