 - Elicit up to 200 trials in structured practice. Target a minimum of 150 trials, but if cumulative session duration reaches 90 minutes, terminate session.
 - After 100 trials, CPP will prompt user to take a 2-minute break. CPP should not resume function until 2 minutes have elapsed. If CPP prompts a break with 5 minutes or less remaining in the session, OK to override the break (press s).
 - Targets
 - To limit variability of practice, only 5 different syllables will be selected for practice in Acquisition. Syllables will be /ʒ/ plus one randomly selected syllable for the other four variants. The same set of syllables will be kept constant across sessions.
 - Practice will occur in blocks of 10 consecutive trials on the same syllable (e.g., 10 /ra/), after which a new syllable will be addressed (e.g., 10 /re/—but note that in the fully blocked condition, the same syllable should occur in two consecutive blocks of 10). CPP should cycle through the set of target syllables, randomizing order of presentation.
 - Scoring and feedback:
 - Clinician scores each production as correct (1) or incorrect (0).
 - For the first 50 trials (i.e., the first block of each syllable), clinician should be cued to provide KP feedback after 5/10 trials, randomly selected from within the biofeedback trials. KP feedback must make reference to both the visual display and to articulator placement; it must also terminate with a direct model for the client to imitate.
 - For the remaining trials, clinician should be cued to provide KP feedback on 3 trials, randomly selected from within the biofeedback trials. KR feedback should be provided on 2 trials other trials, randomly selected. KR feedback can be verbalized but does not have to be (i.e., text presented by CPP alone is sufficient).
 - Cue biofeedback for the first 8/10 trials in each block.
 - In each block of 10 trials, the 9th trial will be flagged for acoustic measurement: a pure tone will sound before the trial, flagging the trial for acoustic measurement via forced alignment. The same trial will be elicited with **no verbal or visual feedback**.
 - The CPP will provide reinforcing messages at the end of each block.
 - If the participant is advancing to a new level, the CPP will report this.
 - Otherwise, CPP should report number of trials completed.
 - Milestone/number of trials message should be paired with a message to encourage continued effort (Growth Mindset).

MASTER PROTOCOL FOR C-RESULTS RCT

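### No model includes the treating clinician, so the biofeedback-versus-MBT tests can exceed their nominal error rate if clinicians are tied to arms, unevenly spread across them, or differ in effect by arm

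*Combined protocol and SAP*

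**What the plan says.** **Delivery.** Section 5 classifies children after the dynamic assessment, "Based on the treating clinicians"' ratings, so there is more than one clinician. In section 7 the clinician gives a model and KP feedback throughout pre-practice, judges when a child may advance, and then gives scheduled KP feedback in structured practice. Of that KP, the protocol says "it must also terminate with a direct model for the client to imitate". Section 9 continues clinician-led treatment for 16 sessions.

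**Allocation.** The target is "Target 55 kids in each of 2 sites (MSU, Syracuse), total n = 110". Section 6 states "Randomization will be proportioned in a 3:3:4 ratio" and "Randomization will be stratified by site and severity". Children are assigned individually, in batches of 10 per combination of site and response category. Clinician is not a stratum.

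**Models.** Section 12 and the Data analysis plan give the primary model as "Random intercepts will be included to reflect the fact that observations are nested within speakers and words", adjusted for site, response category, day and pre-treatment accuracy. For the secondary model the Data analysis plan says "Random intercepts for speaker, item (the 50 target words making up the probe measure), and listener will be included". The survey model is described as similar. No clinician term, fixed or random, appears in any of them.

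**Not stated.** The number of clinicians, how they are assigned to children, whether each delivers all conditions, whether a child keeps one clinician, and the significance level. Tests are two-sided.

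**The concern.** Children treated by the same clinician share that clinician's skill. The plan treats the naïve listener who rates a recording as a source of variance, but not the person who delivers the treatment. Site adjustment removes only differences between sites.

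Two mechanisms can carry clinician differences into the treatment contrast. First, if each clinician works in one arm, or mostly in one, clinician and arm are wholly or partly confounded. Second, if clinicians work in all arms but are better at one method than the other, that clinician-by-arm variation enters the contrast directly. The second is plausible, because KP in the biofeedback arms must refer to the visual display as well as to articulator placement.

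In either case the planned standard error is too small for the overall biofeedback-versus-MBT test. The same holds for the time-by-group tests of the secondary and survey outcomes if clinicians differ in the improvement they produce. The Data analysis plan reads efficiency and effectiveness from whether the primary and secondary outcomes show a difference, so an inflated error rate in either would reach the trial's stated conclusion.

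**Working it through.** **Inputs from the documents.** N = 2 × 55 = 110. The 3:3:4 ratio gives 33:33:44, so pooled biofeedback versus MBT is 66:44, or 33:22 per site. There is no stated power, effect size, SD, significance level or intraclass correlation (ICC) to reproduce.

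**Assumptions.** Nominal two-sided 5%; clinician share of child-level variance (ICC) 0.02 to 0.10; 2 to 6 clinicians per site. The analysis is on child-level outcomes adjusted for site, with no clinician term.

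**1. Clinicians nested in arm.** With m1 and m0 children per clinician in the biofeedback and MBT arms:

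Inflation D = {[1 + (m1 − 1)ICC]/66 + [1 + (m0 − 1)ICC]/44} / (1/66 + 1/44) = 0.4[1 + (m1 − 1)ICC] + 0.6[1 + (m0 − 1)ICC]

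Actual error rate = 2[1 − Φ(1.96/√D)]

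Example: 2 clinicians per site, one per arm, so m1 = 33 and m0 = 22. At ICC 0.05, D = 0.4 × 2.60 + 0.6 × 2.05 = 2.27. The true SE is √2.27 = 1.51 times the model SE, and the error rate is 19.3%.

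Formula results, with simulation (4,000 runs per cell) in brackets:

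| Clinicians per site (biofeedback + MBT) | ICC 0.02 | ICC 0.05 | ICC 0.10 |
|---|---|---|---|
| 2 (1 + 1) | 11.0% (11.0%) | 19.3% (19.7%) | 29.8% (31.6%) |
| 3 (2 + 1) | 9.5% (9.5%) | 15.9% (17.1%) | 24.8% (25.7%) |
| 5 (3 + 2) | 7.4% (7.5%) | 11.0% (11.3%) | 16.6% (16.7%) |

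A further simulation (3,000 runs per cell, 3 to 6 clinicians per site) gave 6% to 10% at ICC 0.02. The formula agrees with its low end: with 6 per site split 4 + 2, D = 0.4 × (1 + 7.25 × 0.02) + 0.6 × (1 + 10 × 0.02) = 1.178, which gives about 7%.

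**2. Clinicians crossed with arm** (simulation, 4,000 runs per cell; 2, 3 or 5 per site):

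| Part of clinician variance that is clinician-by-arm | Share 0.02 | Share 0.05 | Share 0.10 |
|---|---|---|---|
| None | 4.4% to 5.3% | 4.6% to 5.5% | 4.2% to 4.8% |
| Half | 5.0% to 6.4% | 7.3% to 9.3% | 8.0% to 13.0% |
| All | 6.0% to 8.3% | 7.9% to 13.8% | 10.8% to 21.1% |

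A hand check of the largest cell: fully arm-specific effects act like separate clinicians in each arm, so with 2 per site m1 = 33/2 = 16.5 and m0 = 22/2 = 11. Then D = 0.4 × 2.55 + 0.6 × 2.00 = 2.22, giving about 19%. The simulated 21.1% is a little higher; it also lets caseloads vary by chance.

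**3. Clinicians unevenly spread across arms.** Simulation gave about 6% to 8% (ICC 0.05 to 0.10; 3 or 5 per site).

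**4. Is a random intercept with the planned likelihood ratio test enough?** Nested in arm, ICC 0.05, with 3, 4 and 6 clinicians per site (500 runs per cell, Monte Carlo error about 1.5 points): the error rate falls from 16.4%, 12.2% and 12.6% to 10.8%, 7.8% and 9.2%. It improves but stays above 5%.

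**5. Would clinician fixed effects do instead?** In the nested layout they are collinear with arm. In the crossed layout (2 per site, clinician-by-treatment SD 0.3) the error rate was 10.8% for the planned model and 11.0% with fixed effects.

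**The case against.** A reader might infer that leaving the clinician out by itself makes the standard error wrong. The documents do not support that. If every clinician treats all arms evenly and clinicians differ only in overall level, the difference is absorbed into between-child variance and affects both arms alike; the error rate stays near 5%.

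The text also leans towards crossing, if anything. Treating clinicians rate the child before randomization, and each batch mixes all three conditions within a site. If the same clinician continues with the child, clinicians are crossed with arms. Nothing suggests arm-specific clinicians. This makes the nested figures the less likely case, but a handover after randomization is possible and the plan does not exclude one. Crossing also leaves clinician-by-arm variation open.

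The primary outcome is well protected in other respects. It is acoustic, taken on trials elicited without feedback, so clinician scoring does not enter it. In Phase 1 the syllables and the feedback schedule are fixed, and scripts and cue documents standardise delivery. Sites check each other's fidelity on one acquisition session per child. All this limits delivery variation without removing it, and fidelity results enter no model.

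Not every test is exposed. Treatment-by-day is a within-child contrast, and a constant clinician effect largely cancels there. Individual delivery is itself inferred from the session procedures; the documents do not state it.

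**Conclusion.** The point stands in conditional form. The plan has several treating clinicians, no clinician term and no balancing of clinicians across arms, and it does not disclose the layout that decides whether this matters. The exposed tests are the overall biofeedback-versus-MBT test and, where clinicians differ in the improvement they produce, the secondary and survey time-by-group tests.

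The error-rate ranges rest on assumed clinician counts, variance shares and significance level, none of which the documents give. They show what could happen, not an estimate for this trial. They also imply no direction: these are two-sided error rates under no average effect, so they are not evidence of bias towards biofeedback. This is a worthwhile, inexpensive improvement to the plan, not a demonstrated fault in its result.

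**What to change.** In section 12 and the Data analysis plan:

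- Prespecify a random intercept for the treating clinician in all three models: the clinician of the session in the primary model, the main clinician in the secondary and survey models. Keep it whatever the model-comparison test says, because it follows from the design.
- In the two pre/post models, let the clinician effect differ by time point. An intercept that is constant over time drops out of the time-by-group contrast.
- Test the treatment effect with a small-sample method, for example REML with Kenward-Roger or Satterthwaite degrees of freedom, or a parametric bootstrap, in place of the plain likelihood ratio test.
- Where clinicians deliver both biofeedback and MBT, add a clinician-by-treatment random slope as a sensitivity analysis. The intercept alone does not capture that variation.
- Report how many clinicians there are and which conditions each delivers. If they are nested in arm, state that clinician and treatment effects are confounded.
- Do not use clinician fixed effects as a substitute, for the reasons in step 5 of the working.

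The cost is SAP wording and one clinician identifier, which session records should hold. With evenly crossed clinicians the intercept costs almost nothing. Otherwise, expect fewer effective degrees of freedom, a somewhat wider interval if clinicians differ, and possible singular fits with very few clinicians. In the extreme case of two per site nested in arm, four clinician means less three coefficients (intercept, site, arm) leave one degree of freedom.
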